5.4.5 Toxicity Management on PrEP

The toxicity management described below relates only to participants on PrEP with FTC/TDF.

In general, the investigators have the discretion to hold study drug at any time if he or she feels that continued study drug use would be harmful to the participant or interfere with treatment deemed clinically necessary according to the judgement of the investigator.

5.4.5.1 Grading System

The grading system is located in the Division of AIDS Table for Grading Severity of Adult and Pediatric Adverse Events (DAIDS AE Grading Table), Corrected Version 2.1, July 2017, which can be found on the Regulatory Support Center (RSC) website:

<https://rsc.niaid.nih.gov/sites/default/files/daidsgradingcorrectedv21.pdf>

5.4.5.2 Discontinuation of PrEP in the Presence of Toxicity

Grades 1 or 2

In general, participants who develop a Grade 1 or 2 AE regardless of relatedness to study drug and that is not specifically addressed below, may continue use of the study drug per protocol.

Grade 3

For participants who develop a Grade 3 AE or toxicity that is not specifically addressed below and is judged to be related to study drug by the study investigator, study drug use should be temporarily discontinued. In general, the investigator should re-evaluate the participant at least weekly for up to 2 weeks to document resolution of toxicity to less than Grade 2. The study drug should be permanently discontinued if improvement to severity \leq Grade 2 cannot be documented within four weeks of receipt of the initial results.

Grade 4

Participants who develop a Grade 4 AE or toxicity that is not specifically addressed below (regardless of relationship to study drug) should have the study drug temporarily discontinued. The investigator should consult with the Protocol Safety Review Team (PSRT) and continue the temporary study drug hold until a recommendation is obtained from the PSRT. In general, study drug use will not be resumed if the Grade 4 AE is considered related to study drug use. If, in consultation with the PSRT, study drug use is resumed and the same Grade 4 AE recurs at Grade 4 level at any time, study drug must then be permanently discontinued.

5.4.5.3 General Criteria for PrEP Discontinuation

Participants may voluntarily discontinue the study drug for any reason at any time. Study investigators will permanently discontinue participants from study drugs per protocol for any of the specific criteria below. Site study investigators may also permanently discontinue participants for reasons not shown here.

A participant will be permanently discontinued from PrEP drug use by the study investigators for any of the following reasons:

- HIV Infection: Such participants will not resume study drug use at any time. Study drug will be held immediately upon recognition of the first reactive HIV test. The study investigator must permanently discontinue study drug if HIV infection is confirmed. A decision to resume study drug in participants who are subsequently confirmed to be HIV-uninfected requires approval of the protocol chair and PSRT.
- Viral hepatitis: Such participants will not resume study drug use at any time.

Any participant who prematurely discontinues study drug should remain in the study and will continue to be eligible for remaining interventions.

Study drug will be temporarily withheld from a participant for any of the following reasons:

- Report of prohibited concomitant medications. Study drug use may resume when the participant reports that he is no longer taking the prohibited medication, provided other reasons for temporary study drug hold or permanent discontinuation do not apply.
- The participant is unable or unwilling to comply with required study procedures, or otherwise might be put at undue risk to their safety and well-being by continuing study drug use, according to the judgement of the study investigator.

5.4.6 Management of Specific Toxicities on PrEP

Specific guidance related to product hold is also noted here as it pertains to the clinical management of toxicities.

- Nausea, Vomiting, and Diarrhea**

Participants with Grade 1 or 2 nausea, vomiting, or diarrhea may be treated symptomatically with hydration, oral antiemetic therapies or antiemetic suppositories at the discretion of the study investigator. The investigator should order any clinically relevant laboratory analyses per his or her judgement.

Participants with \geq Grade 3 nausea, vomiting, or diarrhea for which an alternative etiology is not established must discontinue the study drugs temporarily until Grade 2 or lower and be treated symptomatically. Should condition(s) not improve to Grade 2 or lower within seven days, the investigator should consult the PSRT for guidance on continuing the temporary discontinuation or progressing to permanent discontinuation of study drugs.

Repeat episodes of these events will be handled independently, and the instruction above will be followed for each event.

- Creatinine Clearance for PrEP**

If the creatinine clearance is <60 mL/min, study drug should be temporarily held and it should be confirmed within one week of the receipt of the results. If the calculated creatinine clearance is confirmed to be <60 mL/min, the study drug must be permanently discontinued. If re-testing yields a result ≥60 mL/min, the study investigator should consult the PSRT for further guidance on resuming study drug use, continuing the hold temporarily, or progressing to permanent discontinuation.

By which the investigator in consultation with the PSRT has determined that the case has stabilized, it may be possible to decrease the frequency of follow-up laboratory testing in addition to resumption of study drug.

- HIV Infection**

Frequent testing for HIV acquisition during the study period will allow prompt cessation of study drug in an HIV-infected participant, minimizing the risk that resistant virus will emerge. Therefore, HIV testing will be performed at PrEP start and every three months thereafter. Any enrolled participants who acquire HIV infection while on PrEP will permanently discontinue study drug but will remain in the study.

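### Read literally, 5.4.6 implies that study drug can restart without required PSRT review after an unexplained Grade 4 nausea, vomiting or diarrhea episode that settles within seven days

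*Combined protocol and SAP*

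**What the plan says.** The general rule is in section 5.4.5.2 of the combined protocol and SAP. It covers "Participants who develop a Grade 4 AE or toxicity that is not specifically addressed below (regardless of relationship to study drug"). For these, the investigator stops drug temporarily, consults the PSRT, and must "continue the temporary study drug hold until a recommendation is obtained from the PSRT". The section adds: "In general, study drug use will not be resumed if the Grade 4 AE is considered related to study drug use". If drug is resumed after PSRT consultation and the same event returns at Grade 4, it must be stopped for good.

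The specific rule is in section 5.4.6. It opens with "Specific guidance related to product hold is also noted here". At Grade 3 or higher, participants with "nausea, vomiting, or diarrhea for which an alternative etiology is not established must discontinue the study drugs temporarily until Grade 2 or lower". The only route to the PSRT is this: "Should condition(s) not improve to Grade 2 or lower within seven days, the investigator should consult the PSRT". On recurrence it says: "Repeat episodes of these events will be handled independently, and the instruction above will be followed for each event".

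In the same section, after a low creatinine clearance that re-tests at 60 mL/min or above, "the study investigator should consult the PSRT for further guidance on resuming study drug use".

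**The concern.** The general Grade 4 rule gives way wherever a later section deals with the event. Section 5.4.6 deals with gastrointestinal events from Grade 3 upward when no other cause has been found, so Grade 4 falls inside it. Its hold lasts only until the episode has eased to Grade 2.

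These are the episodes in which drug-relatedness is a live question. Section 11.3.2 lists nausea, vomiting and diarrhea among the possible effects of FTC/TDF, and 5.4.5.2 says drug is generally not resumed after a related Grade 4 event. If the seven-day rule applies to Grade 4 as written, that judgement can stay with the site alone, and a second or third such episode starts the same cycle again. What is at stake is a second opinion before re-exposure in a small and uncounted set of PrEP users. The study's estimates are not at stake.

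**Working it through.** The plan states no figure on this point, so the check is a rule trace.

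**Step 1: which rule governs.** The event is Grade 4 vomiting with no other cause established. Section 5.4.5.2 excludes events specifically addressed later. Section 5.4.6 addresses this event type at Grade 3 or higher with no established cause. On the literal text, 5.4.6 governs.

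**Step 2: when the hold ends.** Section 5.4.6 makes the hold temporary, until Grade 2 or lower. Nothing in the section expressly authorises restart. It is implied by a temporary hold with a defined end.

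**Step 3: whether the PSRT is reached.** The trigger is failure to improve within seven days. An episode that improves in time does not meet it.

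**Step 4: whether another section restores the requirement.**
- Section 5.4.5 gives the investigator discretion to hold drug.
- Section 5.4.5.3 requires a hold when the investigator judges continued use an undue risk, and lets the site stop drug permanently.
- Section 9.0 has the principal investigators and project coordinators review adverse event reports.
- Sections 9.2.2 and 9.3.1 send events meeting the SAE definition to the IRB and the NIH project officer within 24 hours.

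None of these makes PSRT review a condition of restart.

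**Step 5: required PSRT reviews before restart, for one Grade 4 episode.** The columns cross cause with time to Grade 2 or lower.

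| Reading | Unexplained, within 7 days | Unexplained, over 7 days | Explained, within 7 days | Explained, over 7 days |
|---|---|---|---|---|
| 5.4.6 displaces the general rule for unexplained episodes only | 0 | 1 | 1 | 1 |
| 5.4.6 displaces it for the event type as a whole | 0 | 1 | 0 | 0 |
| 5.4.6 only adds to 5.4.5.2 | 1 | 1 | 1 | 1 |
| With the fix below | 1 | 1 | unchanged | unchanged |

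Both displacement readings give 0 in the first column. The supplementary reading gives 1. A site could follow either in good faith.

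**Step 6: recurrence.** Under 5.4.5.2, a return of the same event at Grade 4 after resumption means a permanent stop. Under 5.4.6, the repeat is treated as new, so successive Grade 4 episodes that each settle within seven days reach neither the PSRT nor a mandatory stop.

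**The case against.** The strongest reply is that the exemption is intended. Section 5.4.5.2 repeats its carve-out at every grade level, so displacement by specific rules is part of the structure. The gastrointestinal rule is also a complete algorithm, with its own threshold, hold, end-point, clock and recurrence sentence. Against the general Grade 3 rule it is the stricter of the two. Its hold is mandatory and needs no judgement that the event is related to drug. It brings in the PSRT at seven days, where the general Grade 3 rule allows four weeks and never mentions the PSRT. All of this stands. It shows that the rule suits Grade 3. It does not show that Grade 4 was considered, because 5.4.6 never separates the two grades.

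The second reply is that the opening of 5.4.6, "Specific guidance related to product hold is also noted here", makes the section a supplement to 5.4.5.2, which leaves no gap. That reading is available, but it gives little effect to the carve-out in the general rule.

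A reader might also infer that this is the protocol's one restart route without PSRT input. The documents do not support that. A related Grade 3 event under 5.4.5.2 and a prohibited-medication hold under 5.4.5.3 both end without it. The fair comparisons are narrower: the general Grade 4 rule requires the PSRT even for unrelated events, and the creatinine rule calls for PSRT consultation after a reassuring re-test.

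**Conclusion.** The point holds as a low-severity wording improvement. On the literal text, required PSRT reviews before restart fall from one to none for an unexplained Grade 4 gastrointestinal episode that settles within seven days, and the permanent stop on Grade 4 recurrence is lost. This rests on two assumptions: that the carve-out in 5.4.5.2 means what it says, and that a temporary hold with an end-point implies restart.

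Three stronger readings should be resisted.
- The protocol does not expressly authorise restart after Grade 4.
- It does not leave these men unprotected: drug must be held at onset, and the safeguards in step 4 apply, although they do not control restart.
- It does not always give explained episodes heavier oversight than unexplained ones. That follows under only one of the three readings.

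The documents give no frequency for such episodes, and Grade 4 is defined in an outside table cited in 5.4.5.1. No count of affected men is therefore claimed. The feasibility and acceptability outcomes do not depend on the point.

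**What to change.** Make three short edits in 5.4.6:

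1. In the nausea, vomiting and diarrhea paragraph, change ≥ Grade 3 to Grade 3.
2. Limit the sentence on repeat episodes to Grade 3 or lower.
3. Add: *Grade 4 nausea, vomiting or diarrhea without an established alternative etiology follows the Grade 4 rule in 5.4.5.2, including the hold until a PSRT recommendation and permanent discontinuation if the same Grade 4 event recurs after resumption.*

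The added sentence points to the general rule as a whole, so recurrence has one consequence. Episodes with an established other cause are left as they stand.

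The cost is a protocol amendment with IRB review (section 11.1), an occasional PSRT consultation, and a somewhat longer time off PrEP for the man concerned, with loss of its protection meanwhile. Some men may not resume at all, because the general rule disfavors restart after a related Grade 4 event and bars it after recurrence. Under 5.4.5.3 they would stay in the study and remain eligible for its other components.

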6.0 MEASURES

A summary table of study measures, and sources for each measure, are provided in the table below. Measurement of tenofovir-diphosphate (TFV-DP) levels will be conducted using liquid chromatography/tandem mass spectrometry methods on DBS samples. TFV-DP level can be translated to an interpretation that indicates mean number of days per week PrEP is ingested over a period of approximately one month. The cutpoint used will be TFV-DP levels considered a surrogate for substantial protection: >700 fmol/punch, a level indicating >4 doses/wk.

Construct	Measure	Data source	Definition	Analysis
PRIMARY OUTCOMES				
Feasibility	Home HIV test orders	Order fulfillment	Proportion of participants sent a home HIV test	Benchmark ≥ 30%
Feasibility	Condom orders	Order fulfillment	Proportion of participants sent 'choice' condom package	Benchmark ≥ 30%
Feasibility	PrEP initiation	Clinical site data	Proportion of participants receiving a PrEP prescription	Benchmark ≥ 20%
Acceptability	Systems Usability Scale ^{126, 127}	Survey	10-item scale, good score is >71	Benchmark: Good score (≥ 71 out of 100)
Acceptability	Ratings for intervention components ⁷²	Survey	Likert acceptability rating for each intervention component (e.g. home HIV test)	Benchmark: Acceptable ratings (≥ 3 out of 5)
PRELIMINARY EFFICACY ASSESSMENT				
HIV testing	HIV testing ^{44,128}	Survey	Change in median number HIV tests	GEE model
Condom use	Condom use ^{44,128}	Survey	Change in proportion of participants reporting always using condoms for anal sex	GEE model
PrEP Use	PrEP use ¹²³⁻¹²⁵	Laboratory data	Number participants with protective levels of TDF-DP	Descriptive report
THEORETICAL ASSESSMENT				
Prevention cascade	PrEP cascade levels ¹²⁹	Survey and clinical site data	PrEP awareness, willingness, prescription, persistence in care, and medication adherence	Descriptive and logistic regression
Theoretical assessment	Unified Theory of Acceptance and Use of Technology (UTAUT2) ¹²¹	Survey	Validated items for performance expectancy, effort expectancy, social influence, hedonic motivation, and habit.	Descriptive and GEE model to estimate SEM parameters
PROCESS OUTCOMES				
Process	New HIV testers	Survey	Proportion changing from never to ever HIV test	Descriptive report
Process	New condom users	Survey	Proportion changing from none to some condom use	Descriptive report
Process	Visits to local health clinics	Survey	Proportion receiving HIV services at health departments	Descriptive report
App use	Time spent in health portal	App paradata	Hours of app health portal exposure	Descriptive report
App use	Consistency of use over time	App paradata	Number with monthly visits to health portal	Descriptive report

7.0 DATA HANDLING AND RECORD KEEPING

7.1 Data Management

Data will be stored in password-protected, encrypted files and secure Sojump servers. Databases of participant identifying information (contact information such as names, emails, and phone numbers) will not be linked to databases with participant data. Participant identifying information will only be linked to whether the participant completes study procedures, needs to be re-contacted, or refuses to participate. The name, email, and phone number of screened men who decline to be scheduled for participation will be removed from the study database after we have asked them questions about why they have a lack of interest in proceeding, unless they request to be contacted for future studies. Access to the identifying information will be on a role-based system: access to identifying information will be restricted to those who need access to perform their work function. Thus, access to identifying information will be restricted to the project coordinator, study staff, and students charged with data entry and scheduling tasks.

7.2 Procedures for Prevention and Addressing Breaches of Confidentiality

The main approach to preventing breaches of confidentiality is to maintain identifying participant information in a single location at each site and to use a non-personally identifying study ID to store all other study data.

To minimize risks to confidentiality, we will provide study data with all appropriate physical and operational security protections. Paper-based data will be stored in a locked cabinet in a locked office, and all data files will have encryption and strong password protection. Access to data will be on a role-based standard; only those study staff, such as principal and co-investigators, data managers, data analysts, study staff, and graduate research assistants, who require access to identifying data to complete their study-related roles will be allowed access. All study staff will complete CITI course modules on human subjects research ethics, socio-behavioral research, and good clinical practice (GCP), will be trained in

security and confidentiality procedures, and will sign a confidentiality agreement before receiving access to any participant data. Any breaches in confidentiality will immediately be reported to the PI and to the IRB. Based on the PI and IRB's recommendation, staff may be retrained or receive disciplinary action. Study staff will follow procedures to minimize indirect disclosure that a participant is participating in an HIV-related research study, or a study that enrolls MSM. For each mode of contact information, including email, telephone, text, and voicemail, we will ask if it is acceptable to leave a non-specific message about participation in a health study. No study-related messages to the participant will ever mention HIV prevention or the nature of the research study. Additionally, all scripts for email, text message, and telephone contact with participants will be reviewed and approved by the IRB before being used for contact with participants.

7.3 Data Capture Methods

Data collected through the online survey interface: Participants will also take surveys through an online survey portal. Data are collected directly on the private server as participants respond to questions. Data will be identified in the system through a study ID. Surveys are conducted using a secure (<https://>) webpage, which means that data entered by participants are encrypted before they are sent through the internet, and are decrypted once received by the survey hosting site. The link between the participant and the participant contact information is held by research staff at Blued.

7.4 Types of Data

Data collected through interactions with the app:

Collection: Participants will use a mobile phone app to get information about HIV prevention and referrals to local services. As participants use the app, data about which they used are entered directly by the participant in the process of interacting with the study app. Data will be recorded as participants request certain app pages or functions. Each time the participant touches a button or navigation function in the app, that piece of data is stored in the administrative portal of the app. Data are stored with an alphanumeric ID that is unique to the participant, and is not stored with identifying information for the participants. The link between the alpha numeric string and the participant contact information is held by research staff at Blued.

Management and Storage: Data are stored in a secure server in the cloud. Access to app data are password protected, and access is role-based. Access to participant data will be limited to study staff approved by the IRB at each site, comprising principal and co-investigators, data managers, data analysts, study staff, and graduate research assistants. Software developers will have access to administrative aspects of the management portal, but will not routinely have access to links to study IDs or personally identifying information (PII). In the case of a “need to know” for study related purposes (for example, duplicate or corrupted files, need to examine specific records to troubleshoot app or data functions) temporary access can be granted to developers, whose access will be limited to the specific records required to resolve the problem. Any developer who needs such access will be required to complete CITI training, complete a data confidentiality form, and be added to the IRB protocol. Access to participant PII will be removed after the specific problem is resolved.

Data collection through online surveys:

Collection: Data will be recorded as participants respond to questions in an online survey portal (Sojump) from a web browser, smartphone or tablet. Data will be identified in the system through a study ID.

Surveys are conducted using a secure (<https://>) webpage. The link between the participant and the participant contact information is held by research staff at Blued.

Management and storage: Sojump takes necessary technical measures to ensure the safety of data stored on Sojump's server, which include, but are not limited to: locked and secured server locations; enterprise firewall protection; RAID real time image preservation of data; regular data backup; and detailed data recovery mechanisms. The access level to the data stored by Sojump will be specified by Blued and Emory; only authorized users with individual password-protected accounts will be permitted to access the data. Without permission of Blued and Emory, Sojump is prohibited from changing the settings. Sojump is prohibited from intentionally or unintentionally disclosing data to any third party. The data confidentiality agreement with Sojump is valid until the Blued and Emory request that the data are destroyed. Data exported to Sojump for analysis will be stored on secure, encrypted servers at Blued in Beijing, China.

Data collected on Case Report Forms (CRFs)

Paper-based case report forms (CRFs) will be completed by site clinicians to capture PrEP-related data. CRFs will be the main data collection tool during PrEP visits. All CRFs will be completed by study clinicians or staff rather than the participants. These forms will be securely stored in participant study binders at the clinical study site, and entered electronically by staff into secure spreadsheets.

